6.3.5. Analysis of safety by frailty status

The safety analysis will be based on the TVC. The analysis of Reactogenicity will be based on the TVC diary card subset.

All safety analyses will be categorised by frailty status.

The following analyses will be performed for safety endpoints:

- The percentage of subjects with at least one local solicited AE, with at least one general solicited AE and with any solicited AE during the solicited 7-day follow-up period will be tabulated with exact 95% CI after each vaccine dose and overall. The same tabulation will be performed for grade 3; related and grade 3 related AEs;
- The percentage of subjects with at least one local AE (solicited and unsolicited), with at least one general adverse event (solicited and unsolicited) and with any AE during the solicited 7-day follow-up period will be tabulated with exact 95% CI after each vaccine dose and overall. The same tabulation will be performed for grade 3, related and grade 3 related AEs;
- The percentage of subjects reporting each individual solicited local and general AE during the solicited 7-day-follow-up period will be tabulated with exact 95% CI. For all solicited symptoms, the same tabulation will be performed for grade 3 solicited AEs and for solicited general AEs with relationship to vaccination;
- Summary of temperature value by half degree increment reported during the 7-day (Days 0-6) post-vaccination period following each dose and overall doses and subjects. The same tabulation for fever with relationship to vaccination will be done;
- The number of days with each individual solicited local and general AE during **the solicited** 7-day follow-up period will be tabulated;
- The percentage of subjects with at least one local solicited AE, with at least one general solicited AE and with any solicited AE reported during the solicited 7-day follow-up period and **lasting beyond this period** will be tabulated with exact 95% CI after each vaccine dose and overall. The same tabulation will be performed for grade 3;

204878 (ZOSTER-064) Statistical Analysis Plan Amendment 1

- The percentage of subjects with each individual solicited local and general symptoms **ongoing beyond the 7-day follow-up period** will be tabulated. The same tabulation will be performed for grade 3;
- The percentage of subjects with at least one report of unsolicited AE classified by the MedDRA Preferred Terms and reported up to 30 days after each vaccination will be tabulated with exact 95% CI. The same tabulation will be performed for grade 3 unsolicited AEs and for unsolicited AEs with a relationship to vaccination.
- Total number/percentages of doses followed by AEs will be tabulated;
- The percentage of subjects with at least one report of serious adverse event classified by the MedDRA Preferred Terms and reported during the whole post-vaccination follow up period will be tabulated with exact 95% CI;
- The proportion of subjects with at least one report of pIMDs classified by the MedDRA Preferred Terms and reported during the whole post-vaccination period (from dose 1 up to study end) will be tabulated with exact 95% CI.

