1. INTRODUCTION

1.1. Background

Varicella-Zoster Virus (VZV) causes two distinct diseases. Varicella (chickenpox) shortly occurs after primary VZV infection and is characterised by systemic illness and a widely disseminated rash. Herpes Zoster (HZ, shingles) occurs when VZV reactivates from latency and typically manifests as a localised, dermatomal rash. The typical HZ rash usually lasts 2 to 4 weeks and is usually accompanied by pain; that is often described as burning, shooting, or stabbing, and pruritus, which can also be severe, may be as common as pain. In some patients, even touching the affected area lightly may cause severe pain, a phenomenon known as allodynia. The most common complication of HZ is postherpetic neuralgia (PHN), defined as pain that persists after the resolution of the HZ rash. Patients affected by PHN typically report constant burning, throbbing, intermittent sharp or electric shock-like pain, or allodynia. PHN tends to improve over a period of months and about 70-80% of cases resolve within 1 year. However, in some persons PHN persists for many years [Dworkin, 2007].

Inclusion of subjects in clinical trials may be biased for various reasons, e.g. inclusion/exclusion criteria, selection of patients by investigators, self-selection of patients. As such, the aim of this study is to explore if the subjects in the ZOSTER-006 and ZOSTER-022 studies were representative of an older adult population. This will be done by exploring the baseline frailty status and quality of life scores of subjects within the studies.

Several studies have demonstrated that the incidence and severity of HZ increases with age [CDC, 2008]. It is also likely that the incidence and severity of HZ is higher in frail subjects. However, as with age vaccine efficacy may somewhat lower in frail subjects. This study will therefore allow a synthesis of the benefit of vaccination in frail subjects, i.e. in terms of increased incidence, vaccine efficacy, safety and immunogenicity.

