1.1.2 ZOSTER-006 and ZOSTER-022

Two GSK-sponsored Phase III studies investigated the effect of GSK's candidate HZ/su vaccine on the incidence of the disease in subjects 50 YOA and older (ZOSTER-006, eTrack number 110390, NCT01165177, started in 2010) [Lal, 2015] and in subjects 70 YOA and older (ZOSTER-022, eTrack number 113077, NCT01165229, started in 2010), respectively [Cunningham, 2016].

An indication in adults ≥ 50 YOA was filed for registration. HZ/su (trade name *Shingrix*) was first approved in Canada and the United States in October 2017.

As part of the study procedures, each subject enrolled in one of these two studies was asked to complete two quality of life (QoL) questionnaires named respectively *SF-36* and *EQ-5D* at predefined timepoints. These questionnaires were to be completed independently from the fact that subjects had HZ or not and provide relevant information about the QoL (functional status, ability to socialize, mental health, etc.) of subjects before they develop HZ (see APPENDIX A and APPENDIX B for samples of the *SF-36* and *EQ-5D* questionnaires).

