		11 FEB 2019

2. STUDY DESIGN

This is a retrospective, observational study, in which pooled data from the ZOSTER-006 and ZOSTER-022 will be analysed. As a consequence no new subjects will be enrolled in this study and no new ICF will be required from study subjects.

In ZOSTER-006 and ZOSTER-022, encoding of Quality of Life (QoL) questionnaires (*SF-36*, *EQ-5D*) was only performed for subjects who developed a suspected Herpes Zoster (HZ) episode during the study. This was done to assess the QoL of subjects who developed suspected cases of HZ between the vaccine group and the placebo group. The remaining study subjects who did not develop suspected cases of HZ completed the questionnaires; however, these questionnaires were never encoded or analysed as part of ZOSTER-006 and ZOSTER-022. The remaining questionnaires will be encoded in ZOSTER-064. These questionnaires will be used, in association with already encoded medical history from each subject, to derive a frailty index and thus assign each subject to a baseline frailty status (non-frail, pre-frail, frail, missing). This will allow efficacy, safety and immunogenicity data to be re-analysed according to frailty status.

The following group names will be used for the statistical analyses:

l	Group order in tables	Group label in tables	Group definition for footnote	
	P	HZ/su	Herpes Zoster subunit vaccine	
ĺ	D	Placebo	Placebo	

The following sub-groups will be used for the statistical analysis:

Table 1 Details of subgroups

Sub-group category	Sub-group order in tables	Sub-group label in tables	Sub-group definition for footnote
Frailty Status	PP -D	Non-Frail	Subjects with frailty index score ≤0.08
	D	Pre-Frail	Subjects with frailty index score >0.08 and ≤0.25
		Frail	Subjects with frailty index score >0.25
		Unknown	Subjects who were not assigned a Frailty Status
Gender	nder M		Male Subjects
		Female	Female Subjects

204878 (ZOSTER-064) Statistical Analysis Plan Amendment 1

Table 2 Details of age and region subgroups

Analysis by age group

ord	b-group Ier in Iles	Sub-group label in tables	Sub-group definition for footnote	Pooled Groups 1 label in tables	Pooled Groups 2 label in tables
PP -D		50-59YOA	50-59 years old subjects	50-59YOA	< 70YOA
	60-69YOA 70-79YOA		60-69 years old subjects	60-69YOA	< 70YOA
			70-79 years old subjects	70-79YOA	≥ 70YOA
		80-89YOA	80-89 years old subjects	≥ 80YOA	≥ 70YOA
		≥ 90YOA	≥ 90 years old subjects	≥ 80YOA	≥ 70YOA

Analysis by country/region

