6.3.2. Vaccine efficacy by frailty status

The vaccine efficacy (VE) of the combined ZOSTER-006 and ZOSTER-022 studies will be based on the mTVC and will be classified by frailty status.

The VE will be estimated separately for each frailty category.

Further details of the model used to calculate the VE is contained in the statistical analysis plans (SAPs) for the ZOSTER-006 and ZOSTER-022 studies.

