6.3.6. Analysis of immunogenicity by Frailty status

The analysis of immunogenicity will be categorised by vaccination group and frailty status. The primary analysis will be based on the ATP cohort for analysis of immunogenicity.

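### The by-frailty efficacy, burden-of-illness, safety and humoral analyses state no age split or adjustment, so differences across frailty categories are likely to reflect age in part

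*SAP*

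**What the plan says.** Four SAP sections present outcomes by frailty.

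- Efficacy (SAP 6.3.2): "The VE will be estimated separately for each frailty category". The model is deferred to the parent-trial SAPs.
- Burden of illness (SAP 6.3.3): case counts, mean scores and follow-up time by frailty category and vaccination group; efficacy with its interval by frailty category.
- Safety (SAP 6.3.5): "All safety analyses will be categorised by frailty status".
- Immunogenicity (SAP 6.3.6): "The analysis of immunogenicity will be categorised by vaccination group and frailty status".

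None of them mentions an age split, an age term or standardisation to a common age mix. Protocol 10.7.6.2.1, 10.7.6.2.2, 10.7.6.4 and 10.7.7 do not either.

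Age does appear elsewhere. SAP section 2 contains "Table 2 Details of age and region subgroups", which pools ages into below 70 and 70 and over. SAP 6.1 gives demographics and mean age by frailty status, and SAP 6.2.1 gives frailty counts by age group. SAP 6.3.1 summarises quality of life by age group. SAP 6.3.4 fits an age-adjusted Cox model in placebo recipients and tabulates confirmed among suspected HZ cases by age group.

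On the role of age, Protocol 1.1 says: "However, as with age vaccine efficacy may somewhat lower in frail subjects". Protocol 1.1.1 gives HZ incidence of about 5 per 1,000 persons per year at ages 50-59 and 10 per 1,000 from age 60.

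**The concern.** Protocol 1.1 sets out to bring together incidence, efficacy, safety and immunogenicity in frail subjects, and Protocol 10.8 says the comparisons are meant to characterise differences between groups. Readers will therefore compare the frail, pre-frail and non-frail columns.

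Frailty is likely to rise with age: 12 of the 41 index items are medical-history conditions, among them cataract, arthritis and congestive heart failure. The documents themselves treat age as related to HZ incidence and possibly to VE. If the frail column is older, a lower antibody concentration, lower reactogenicity, higher serious adverse event rate or higher HZ rate in that column could come from frailty, from age or from both. As written, the tables would not separate them. By contrast, SAP 6.3.4 adjusts every candidate predictor of HZ for age, but that model is limited to placebo recipients and the SAP does not list frailty status among its predictors.

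**Working it through.** The plan states no figure for this point, so there is none to reproduce. The checks below ask where an age difference would come from and how far it would carry into the tables.

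**1. Source of the age difference**

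Input from the documents: about 5% frail (SAP 6.3.6.2). Assumed: p, the pooled share aged 70 or over, and RR, the ratio of frailty prevalence at 70 and over to that below 70.

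- Prevalence below 70: f0 = 0.05 / (1 − p + RR × p). Prevalence at 70 and over: f1 = RR × f0.
- Share aged 70+ among the frail: f1 × p / 0.05. Among everyone else: (1 − f1) × p / 0.95.

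Example with RR = 2 and p = 0.60: f0 = 0.05 / 1.6 = 0.03125 and f1 = 0.0625. The shares are 0.0375 / 0.05 = 75.0% and 0.9375 × 0.60 / 0.95 = 59.2%, a gap of 15.8 points.

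| RR | p = 25% | p = 50% | p = 60% | p = 75% |
|---|---|---|---|---|
| 1 | 0 | 0 | 0 | 0 |
| 1.5 | 8.8 | 10.5 | 9.7 | 7.2 |
| 2 | 15.8 | 17.5 | 15.8 | 11.3 |
| 3 | 26.3 | 26.3 | 23.0 | 15.8 |

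(Gap in percentage points.) With no link between frailty and age the gap is zero at any p. With a link it is about 7 to 26 points, and it does not grow steadily as more subjects aged 70+ are added.

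**2. HZ incidence**

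Inputs from Protocol 1.1.1: 5 per 1,000 per year at 50-59 and 10 from age 60. Assumed: s, the share aged 50-59 in a category, and no frailty effect at a given age.

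- Crude placebo rate = 5s + 10(1 − s) = 10 − 5s.
- s = 30% non-frail and 10% frail: 8.5 against 9.5, ratio 1.12.
- s = 20-40% non-frail and 5-20% frail: ratio from 9.00 / 9.00 = 1.00 to 9.75 / 8.00 = 1.22.

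**3. Vaccine efficacy**

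Treating VE in a category as a mean weighted by age share, spurious difference = (VE gap between age groups) × (difference in age mix). With assumed VE gaps of 0, 5 or 10 points and age-mix differences of 5 to 25 points, it runs from 0 to 0.10 × 0.25 = 2.5 points.

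**4. A solicited symptom**

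All inputs assumed: incidence 85% below 70 and 70% from 70; frail prevalence 3% and 8%; non-frail prevalence 55% and 35%. Difference = 15 points × (70+ share in frail − 70+ share in non-frail).

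- Pool 60% aged 70+: frail 0.048 / 0.060 = 80.0%, non-frail 0.21 / 0.43 = 48.8%; 15 × 0.312 = 4.7 points.
- Pool 50%: 72.7% and 38.9%; 5.1 points.
- Pool 70%: 86.2% and 59.8%; 4.0 points.

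These inputs imply 5.5% to 6.5% frail overall, close to the SAP's 5%.

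**The case against.** The strongest reply is that the study is descriptive. Protocol 10.8 asks for cautious interpretation, the safety objective is to describe, and SAP 6.3.6.1 rules out inferential humoral analysis. Outcomes in frail subjects at their actual ages answer that objective, and separating frailty from age is a further question. Readers will also see the age imbalance in the tables of SAP 6.1 and 6.2.1. This has force: it makes the point an improvement rather than an error. But showing an imbalance does not remove it, and a caution does not tell the reader how much of a difference is age.

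A second reply is that the parent-trial SAPs and the table annex were not supplied and could hold age terms or splits. That stands as an uncertainty. An age-stratified VE model would adjust within a frailty category but would not equalise the age mix between categories.

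Three stronger readings are tempting and are not supported.

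- *Pooling makes the frail older.* Protocol 1.1.2 describes one trial "in subjects 50 YOA and older (ZOSTER-006" and the other "in subjects 70 YOA and older (ZOSTER-022", and SAP section 2 says "pooled data from the ZOSTER-006 and ZOSTER-022 will be analysed". A reader might infer that the design itself ages the frail category. Pooling adds older subjects to every category; check 1 shows that the gap comes from the frailty-age link, and it would arise in ZOSTER-006 alone.
- *VE within a frailty category is biased.* Frailty status is fixed before dose 1, and this point gives no reason for vaccine and placebo recipients in the same category to differ in age.
- *The plan ignores age.* It uses age in SAP 6.1, 6.2.1, 6.3.1 and 6.3.4. The gap is confined to the outcome tables by frailty.

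**Conclusion.** The point holds for comparison across frailty categories. The stated analyses carry no age split or adjustment, and if frailty rises with age, as is likely, part of any difference across categories will be age.

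The likely size is modest: an HZ rate ratio of 1.00 to 1.22, a VE difference of 0 to 2.5 points, and about 4 to 5 points for a symptom with the assumed age gradient, all with no frailty effect. Only the 5% frail and the two HZ rates come from the documents. The age mixes, the strength of the frailty-age link, the VE gap and the symptom rates are assumptions. The conclusion would weaken if the unseen parent SAPs or table annex already provide age splits; in that case the SAP text should say so.

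**What to change.** Keep the all-ages tables. In SAP 6.3.2, 6.3.3, 6.3.5 and 6.3.6.1 add the key by-frailty outputs within the two pooled age groups of SAP Table 2, below 70 and 70 and over:

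- VE and HZ incidence rates;
- burden of illness;
- any and grade 3 solicited symptoms;
- any serious adverse event;
- anti-gE geometric mean concentration.

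At minimum present them for 70 and over, where both trials contribute. A two-group split will not remove every age difference: the group below 70 still mixes ages 50-59 and 60-69, between which the protocol's HZ rate doubles.

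No new data are needed. The cost is more tables, and sparse cells for frail subjects below 70. Overall, 5% of about 30,000 is about 1,500 frail subjects before loss of centres. In the humoral subset of about 2,800 (Protocol 10.4.2), 5% is 140 frail. If 20% of those are below 70, as in the 60% case of check 4, that is about 28 across both vaccination groups. Such cells can be shown with their wide intervals or omitted, leaving the 70-and-over table.

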6.2.1. Inclusion criteria for the study data encoding

- All subjects enrolled in ZOSTER-006 and ZOSTER-022 (See Section 7.2 and 8.3.1)
- Subjects who died or were lost to follow-up during ZOSTER-006 and ZOSTER-022 will be considered for enrolment in ZOSTER-064 and their data/questionnaires up to that point will be used.

See Section 8.1 for site specific subject lists.

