10.6. Derived and transformed data

10.6.1. Handling of missing data

For a given subject and a given measurement, missing or non-evaluable measurements will not be imputed for the analysis. The missing endpoint and censoring are supposed to occur independently, and the pattern of the missingness being either Completely At Random (MCAR) or Missing At Random (MAR) only.

For the analysis of solicited symptoms, missing or non-evaluable measurements will not be replaced. Therefore, the analysis of the solicited symptoms based on the TVC will include only subjects/doses with documented safety data (i.e., symptom screen/sheet completed).

For the analysis of unsolicited AEs/SAEs/concomitant medication, all vaccinated subjects will be considered and subjects who did not report an event will be considered as subjects without an event.

For a given subject and a given immunogenicity measurement, missing or non-evaluable measurements will not be replaced. Therefore, an analysis will exclude subjects with missing or non-evaluable measurements.

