4.2. Secondary endpoints

- SF-36 and EQ-5D scale scores.
 - At months 0, 14, 26 and 38.
- Confirmed HZ cases.
 - Incidence of HZ cases during ZOSTER-006 and ZOSTER-022 for subjects in the modified Total Vaccinated Cohort (mTVC).
- HZ Burden of Illness.
 - HZ Burden of Illness score for subjects in both ZOSTER-006 and ZOSTER-022 as calculated from the Zoster Brief Pain Inventory (ZBPI)

204878 (ZOSTER-064) Statistical Analysis Plan Amendment 1

- Solicited local and general symptoms collected in ZOSTER-006 and ZOSTER-022:
 - Occurrence, intensity of each solicited local symptom within 7 days (Days 0-6) after each vaccination, in subjects included in the 7-day diary card subset;
 - Occurrence, intensity and relationship to vaccination of each solicited general symptom within 7 days (Days 0-6) after each vaccination, in subjects included in the 7-day diary card subset.
- Unsolicited adverse events (AEs) collected in ZOSTER-006 and ZOSTER-022:
 - Occurrence, intensity and relationship to vaccination of unsolicited AEs during 30 days (Days 0 - 29) after each vaccination, according to the Medical Dictionary for Regulatory Activities (MedDRA) classification in all subjects.
- Serious Adverse Events (SAEs) collected in ZOSTER-006 and ZOSTER-022.
 - Occurrence and relationship to vaccination of all SAEs from Month 0 to Month 14 in all subjects;
 - Occurrence of SAEs related to study participation or to a concurrent GSK medication/vaccine during the entire study period in all subjects;
 - Occurrence of any fatal SAEs during the entire study period in all subjects.
- Occurrence of pre-defined AEs collected in ZOSTER-006 and ZOSTER-022
 - Occurrence and relationship to vaccination of any potential Immune Mediated Diseases (pIMDs) during the entire study period in all subjects.
- Humoral Immunogenicity of the study vaccine in subset of subjects from ZOSTER-006 and ZOSTER-022.
 - Anti-gE and anti-VZV Ab concentrations as determined by Enzyme-linked Immunosorbent Assay (ELISA), in a subset of subjects at Months 0, 3, 14, 26 and 38.

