6.3.3. HZ Burden of illness by frailty status

The pooled HZ burden of illness (BOI) scores from the ZOSTER-006 and ZOSTER-022 studies will be presented by frailty category.

The number of subjects with a confirmed HZ episode, the mean BOI scores and the total follow-up time will be presented by Frailty category and vaccination group. The burden of illness vaccine efficacy and 95% confidence intervals (CIs) will be presented by frailty category. This analysis will be carried out for subjects in the mTVC.

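### Whole-study pIMDs are shown by frailty only as a crude proportion, with no follow-up time, so unequal early exit would bias the comparison across frailty categories

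*SAP*

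**What the plan says.** Under SAP 6.3.5, "The safety analysis will be based on the TVC" and "All safety analyses will be categorised by frailty status". For pIMDs, the section lists the proportion of subjects with at least one report, by Preferred Term, "reported during the whole post-vaccination period (from dose 1 up to study end) will be tabulated with exact 95% CI". For SAEs it lists the percentage of subjects with at least one, "reported during the whole post-vaccination follow up period will be tabulated with exact 95% CI". No rate, person-time or time-to-event summary is listed for safety. In the decimals table (SAP 7.6), IR, T and T/N appear only under efficacy. SAP 9 adds that SAEs and pIMDs will not be described in detail, so these percentages carry the long-term safety description.

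On subjects with incomplete follow-up, Protocol 10.6.1 says of unsolicited AEs and SAEs that "all vaccinated subjects will be considered and subjects who did not report an event will be considered as subjects without an event". Protocol 6.2.1 says "Subjects who died or were lost to follow-up during ZOSTER-006 and ZOSTER-022 will be considered for enrolment in ZOSTER-064", with their data used up to that point.

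Follow-up time by frailty is planned in one place, the burden-of-illness output of SAP 6.3.3, where "the total follow-up time will be presented by Frailty category and vaccination group". That output uses the mTVC.

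The endpoints differ in their windows (SAP 4.2). pIMDs are an endpoint for the entire study. All-cause SAEs are an endpoint from Month 0 to Month 14. After that, only SAEs related to study participation or to a concurrent sponsor product, and fatal SAEs, are endpoints.

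**The concern.** A crude proportion compares groups fairly only if they were observed for similar lengths of time. The pIMD window runs over several years, since scheduled assessments go to Month 38. Frailty categories are built from accumulated illness and poor function, so equal follow-up across them cannot be taken for granted.

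A subject who withdraws in the first year without a pIMD counts the same as one observed to study end without a pIMD. If such exits are more common in one category, its percentage falls for that reason alone. The confidence interval does not show this, and without follow-up time in the table a reader cannot judge it.

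Protocol 1.1 says the study should bring together the benefit of vaccination in frail subjects, safety included, so the frail versus non-frail safety description is one that readers will use.

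**Working it through.** The documents give no pIMD rate, withdrawal rate, mortality or follow-up time by frailty, so there is no planned figure to reproduce. What follows is an illustration with assumed rates.

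**Inputs**
- Full-follow-up pIMD risk p = 1% (assumed).
- Proportion leaving early d, by withdrawal or loss (assumed, 5% to 40%).
- Window T = 38 months (assumed from the last scheduled questionnaire). T cancels below.
- Constant event hazard λ and exit hazard μ, independent of each other. Protocol 10.6.1 itself assumes independent censoring.

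**Formulas**
- λT = −ln(1 − p) and μT = −ln(1 − d).
- Expected crude proportion = λ/(λ + μ) × [1 − exp(−(λ + μ)T)].

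**Worked case**, λT = −ln(0.99) = 0.01005:
- d = 10%: μT = 0.10536. Crude = 0.01005/0.11541 × (1 − 0.99 × 0.90) = 0.08708 × 0.109 = 0.949%.
- d = 20%: μT = 0.22314. Crude = 0.01005/0.23319 × (1 − 0.99 × 0.80) = 0.04310 × 0.208 = 0.896%.
- Ratio, 20% exit against 10%: 0.896/0.949 = 0.944, although the true risks are equal.

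| Early exit | Crude % when true risk is 1% | Relative understatement |
|---|---|---|
| 5% | 0.975 | 2.5% |
| 10% | 0.949 | 5.1% |
| 20% | 0.896 | 10.4% |
| 30% | 0.841 | 15.9% |
| 40% | 0.783 | 21.7% |

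The relative understatement is about half the exit proportion and hardly changes for true risks from 0.5% to 30%.

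| Exit, non-frail | Exit, frail | Crude frail/non-frail ratio (true ratio 1) |
|---|---|---|
| 5% | 10% | 0.974 |
| 10% | 20% | 0.944 |
| 10% | 30% | 0.886 |
| 20% | 20% | 1.000 |
| 20% | 10% | 1.059 |

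The last row shows that the sign depends on which category leaves more often.

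**Vaccine versus placebo within a category.** With equal exit in both arms and a true rate ratio of 2, the crude ratio is 1.99 at 10% exit and 1.99 at 30%. It is also 1.99 with no exit.

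**Does a rate repair it?** Mean person-time = [1 − exp(−(λ + μ)T)]/(λ + μ). At 10% exit this is 0.109/0.11541 × 3.167 = 2.991 years, and at 20% it is 0.208/0.23319 × 3.167 = 2.825 years. Dividing each crude proportion by its person-time gives 3.17 per 1,000 person-years in both cases, so the artificial difference disappears.

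**Random error for scale.** SAP 6.3.6.2 expects about 5% frail, and Protocol 10.4 gives about 30,000 subjects: 0.05 × 30,000 = 1,500, or 750 per arm if allocation was 1:1 (assumed). Eight events in 750 give 1.07%, exact 95% CI 0.46% to 2.09%.

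**The case against.** The strongest case on the other side has five parts.

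- **Deaths.** A reader might infer that subjects who died are counted as event-free for SAEs, so that the any-SAE percentage understates risk in frail subjects. The documents do not support this. SAP 4.2 has as an endpoint "Occurrence of any fatal SAEs during the entire study period in all subjects", so a subject who dies has an SAE, and higher mortality raises the any-SAE percentage. For pIMDs, death is a competing event. With no other loss, the crude proportion equals the cumulative incidence actually experienced, and it falls short only of a hypothetical risk without death. Genuine understatement comes from withdrawal and loss. This objection stands.
- **Direction.** It is tempting to say the understatement is greatest in frail subjects. No document gives exit by frailty, and the direction reverses if they leave less often. This stands too, but it is also a reason to show the follow-up.
- **Precision and purpose.** Random error in the frail group exceeds a bias of this size, the objective is descriptive, and person-years do not remove differences in age and comorbidity. All true. The confidence interval, however, displays the random error and not this bias.
- **Follow-up is shown elsewhere.** The burden-of-illness table uses the mTVC, which leaves out subjects without a second vaccination and so omits some of the earliest leavers. It does not stand in for person-time from dose 1 in the TVC.
- **Unseen rules.** Safety derivations are held in the parent-study SAPs (SAP 7.1.3), and the no-report rule in Protocol 10.6.1 does not name pIMDs. Those SAPs may add detail. Even so, a plain proportion of TVC subjects treats non-reporters in the same way, and the outputs listed in SAP 6.3.5 contain no rate.

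**Conclusion.** The point holds for pIMDs, as a cheap improvement rather than a serious flaw. The only planned whole-study pIMD summary ignores how long each subject was observed, and nothing in the safety outputs lets a reader see whether follow-up differed by frailty.

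The size depends on exit rates that are assumed throughout. With 20% against 10% early exit and equal true risk, the frail/non-frail ratio reads about 0.94. A true rate ratio of 1.20 would read about 1.20 × 0.944 = 1.13. With equal exit there is no bias, and with less exit in frail subjects it goes the other way. Vaccine versus placebo within a category is nearly untouched if exit is equal in both arms.

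The point should not be extended to say that the any-SAE percentage hides deaths, or that risk in frail subjects is known to be understated. Nor does the several-year argument carry over to all-cause SAEs, which are an endpoint only to Month 14.

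**What to change.** In SAP 6.3.5, beside the crude pIMD proportion, add by vaccination group and frailty category:
- person-years at risk in the TVC, from dose 1 to first pIMD, death, withdrawal or study end, whichever comes first;
- the first-pIMD rate per 1,000 person-years, with an exact Poisson 95% CI.

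Keep the crude proportion. If a person-time rate is also wanted for all-cause SAEs, limit events and person-time to Month 0 to Month 14. Running it to study end would add years in which most SAEs are not an endpoint and would dilute the rate by an amount that depends on length of follow-up.

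The cost is a paragraph of SAP text and a few table columns. No new data are collected, because follow-up time is already derived for the burden-of-illness output, but it must be derived again for the TVC from dose 1. Two limits remain. Rates in the frail group will be imprecise, and a single rate summarises the window well only if the pIMD rate is roughly constant over time.
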